3.3. Code identification of the device

IPG: A-1-I-#

Lead A-1-L-#

Charger: A-1-C-#

Programmer: A-1-P-#

Strap: A-1-S-#

3.4. Intended purpose

3.4.1. Indication

The baroloop device is indicated for the treatment of hypertension.

3.4.2. Intended patient group

The intended patient group is adults greater than or equal to 18 years of age.

3.4.3. Target/intended body parts

The implantable pulse generator (IPG) is implanted subcutaneously in the left upper chest outside the rib cage, and the Lead is tunneled subcutaneously from IPG on the chest wall to the left side of the neck. The Cuff is wrapped around the left vagus nerve in the neck.

3.4.4. Target user profile

Medical professional surgical implantation of the device - surgeon: The implantable parts of the stimulator will be used by surgeons who are trained and experienced in the field of neurosurgery or in carotid sheath-related surgical procedures (e.g. vascular surgeons or otorhinolaryngologists).

Medical professional adjustment of vagal nerve stimulation to control blood pressure - physician: the physician should be board-certified and have experience and expertise treating hypertension.

3.4.5. User environment

The Charger is used in a professional environment (hospital or doctor's office).

Programmer is used in a professional environment (hospitals, clinics, doctors' offices)

3.5. Mode of action of the device and principles of operation of the device

baroloop uses adjustable electrical pulses to neuromodulate the left vagus nerve. The pulses generated by the implantable pulse generator (IPG) are delivered selectively over the neuroelectronic interface of the Cuff. The cathodes of the Cuff surround the vagus nerve.

The Programmer is used to select cathodes to stimulate segments of the nerve. Stimulation of an appropriate segment of the vagus nerve triggers the baroreflex and lowers blood pressure.

3.6. Contraindications

Vagotomy (no usage of device after bilateral or left cervical vagotomy possible)

Diathermy – The use of shortwave diathermy, microwave diathermy, or therapeutic ultrasound diathermy on patients with an implanted VNS device is contraindicated

Baroreflex failure or autonomic neuropathy

Symptomatic, uncontrolled bradyarrhythmia's

Atrioventricular block of any grade

Patients who are treated with Pacemaker and/or implantable defibrillators

Presence of a vagus stimulator

Patients who require magnetic resonance imaging (MRI)

Occupational exposure to high levels of non-ionizing radiation that may interfere with therapy

Patients with a limited ability to read, understand and execute adjustment procedures (for example, persons suffering from dementia)

3.7. Warnings

The warnings are also included in the manuals.

General warnings, warnings and precautions must be followed to avoid system failures.

The baroloop system is indicated only for the treatment of hypertension. Implantation for other treatments or indications has not been tested and is NOT permitted.

The baroloop system must be implanted by surgeons experienced and trained in the field of neurosurgery or in carotid sheath-related surgical procedures.

The physician who is treating the patient with baroloop system should be board-certified and have experience and expertise treating hypertension.

Patients with an implanted baroloop system should not be subjected to MRI. The baroloop system has not been tested for MRI use. Exposure to the magnetic field in an MRI might result in dislocation, heating of metallic components of the device, induced electrical currents in the Lead and/or tissue damage.

Shortwave diathermy, microwave diathermy, or therapeutic ultrasound (all of which may result in diathermy) should not be used on patients in whom the baroloop system has been implanted. Energy generated by diathermy may be transferred through implanted baroloop system and could lead to tissue or nerve damage or result in severe injury or death. Furthermore, the IPG may be damaged by the energy generated by diathermy.

Ultrasound energy may damage the Lead of the baroloop system. Therefore, physicians must avoid using ultrasound focused on regions containing implanted components of the baroloop device.

Extracorporeal lithotripsy may damage the IPG. Therefore, physicians must avoid using extracorporeal lithotripsy in the region containing the implanted IPG.

Radiation therapy may damage the baroloop system. Physicians must avoid using radiation therapy in the region of the implanted components of the baroloop system.

X-ray and CT Scans may affect the IPG, if the IPG is active and turned on. Physicians must be aware that the baroloop device must be turned off prior obtaining X-rays or CT scans in the region of the implanted components of the baroloop device.

Images obtained using X-ray and CT Scanning may be influenced by the presence of implanted components of the baroloop system when the components of the baroloop system overlay or distort the X-ray or CT scan images.

Magnetic fields may influence the function of the IPG and temporarily interrupt therapy by the baroloop system.

Potential effects of the baroloop system on the function of other implanted devices, e.g. cardiac pacemakers, defibrillators and other electronic devices and neurostimulators, are unknown. Therefore, use of the baroloop system in individuals with any of the aforementioned devices is not recommended. Moreover, the aforementioned implanted devices could affect the functionality of the baroloop system.

Physicians must advise each patient or the patient's caregivers to avoid manipulation of the baroloop system through the skin. Manipulation of any implanted components of the baroloop system could damage the device, cause lead migration and/or skin damage, or damage the vagus nerve.

Physicians should advise the patient that external mechanical forces may damage the implanted components of the baroloop system. For this reason, physicians should discuss with each patient his or her activities so that physical activities that might damage the baroloop system may be avoided.

Physicians must advise each patient that strong electromagnetic fields may influence the performance of the implantable components of the baroloop device. Sources of strong electromagnetic fields can lead to system failures or disrupted communication between Charger and IPG.

Physicians must advise each patient that excessive movement during the ingrowth phase may displace implanted components of the baroloop system and must be avoided.

Physicians must advise each patient or the patient's caregivers that the Charger should not be covered with any material (e.g., a blanket, sheet, or clothing) that could prevent heat loss from the Charger during the charging process. If the patient feels any discomfort during charging of the IPG through the skin, the charging should be stopped.

3.8. Risk class of the device

The baroloop device is an active implant intended for use in humans for the treatment of hypertension.

The baroloop device is a programable vagal nerve stimulator for the monitoring, treatment and alleviation of hypertension. Its mode of action is electrical and mechanical, and it does NOT rely on any biological, immunological or metabolic means to alter the function of the human body. It contains no products derived from animal or human tissue.

The Lead + IPG and the Charger are Class III devices and the Programmer Software is also a Class III device.

3.9. Novel features

Selective stimulation of segments of the left vagus nerve for blood pressure reduction.

3.10. Accessories of the device

The Programmer is intended to be used together with the stimulator platform to directly assist medical functionality of the IPG (via the Charger) in terms of its intended purpose.

The Strap is an adjustable, external holder that keeps the Charger in close proximity to the IPG during battery charging and data transfer.

[figure not shown]
3.11. Available configurations of the device

[figure not shown]
The baroloop system consists of the IPG, the Lead and the Charger. The Programmer is provided to the professional medical user and can be used in combination with more than one baroloop system.

[figure not shown]
[figure not shown]
3.12. General description of key functional elements

Lead

The Lead is an assembly that consists of the Cuff, the Pill, the Cable, and the Connector. It is used to transfer electrical energy from the IPG to the vagus nerve.

[figure not shown]

Cuff
 
The Cuff is the interface between the epineurium of the vagus nerve with the stimulator. It contains 12 fractal-shaped, cathodic electrode contacts and two anodal rings. The substrate of the Cuff is made of flexible polyimide, and a flexible extension of the Cuff, the Ribbon, connects the electrode contacts to the Pill. The Cuff is pre-shaped and wraps (curls) around the nerve in conformity with preset shape of the Cuff. The implantation of the Cuff is suture-less.
	

Pill
 
The Pill consists of a ceramic interface with a silicone overmoulding. The ceramic element is the electrical interface between the Cuff and the Cable. The silicone overmoulding has two notches in its external surface that may be used to facilitate surgical fixation of the Pill near the neurovascular bundle that contains the vagus nerve.
	

Cable
 
The Cable passes subcutaneously from the Cuff to the IPG and is used for transmission of the electrical signals to and from the Cuff electrode to the IPG.
	See above.

Connector
 
The Connector is the electrical interface between the Lead and the IPG.
	

Suture Sleeve
 
The Suture Sleeves provide anchoring brackets to fix the cable to the surrounding tissue.
	

IPG The IPG is the active part of the baroloop stimulator system. It generates the stimulation pulses, which are transmitted via the Lead to the vagus nerve. The IPG also records information related to the impedance and continuity of each electrode element in the Cuff and the heart rate. The IPG contains a rechargeable battery as an energy source and a wireless power transmission module for charging.	
Torque key The torque key is a tool for fastening or loosening the fixation screws to fix the Connector in the header of the IPG.	
Charger The Charger is an external device, which is used to program the IPG, to transfer recorded data from, and electrical energy (recharge) to the IPG. It acts as the interface between the implanted IPG and the Programmer. The power for the Charger is derived from a rechargeable battery. The Charger communicates wirelessly with the IPG and allows configuration of the IPG through the Programmer.	 Charger

The Charger fits into an adjustable, external Strap to hold the Charger close to the IPG during charging, programming, and data transfer.

Programmer (software)

The Programmer is used to adjust the stimulation parameters of the IPG. For this purpose, it communicates with the Charger, which is the interface to the IPG. The Programmer itself does not establish a direct connection to the IPG. The programming device used will be obtained from third-party manufacturer and consists of a computer or tablet. The software is developed by neuroloop.

3.13. Device Accountability

Access to baroloop System inventory will be controlled and will be housed in a secure location. Records will be maintained to document the physical location of inventory from shipment / removal from the Sponsor's facility through use and / or return or disposal.

The site will be responsible for keeping a Device Accountability Log provided by the Sponsor or its designated representative in which will be recorded, at a minimum, date of receipt, baroloop System identification number, expiration date, date of use, subject unique identity code and date of disposal of the device.

If there is a product malfunction or other need to return the system or system components to the Sponsor, the Sponsor should be contacted for safe product disposal and / or return details.

NOTE: Please complete a Device Malfunction Form and immediately email to [contact] or fax to [contact] if a device malfunction / failure has occurred.

The Investigator is responsible for ensuring that the investigational devices are used only under the Investigator's supervision and are only used according to this protocol and any approved amendments. The Investigator will not supply an investigational device to any person not authorized to participate in the study. The Investigator shall document in the Case Report Forms the lot numbers of the devices used during each case.

3.14. Return of Devices

All unused investigational devices will be returned to the study Sponsor upon completion of the clinical study. Any investigational device that fails to perform correctly will be returned to the study Sponsor or its designated representative for analysis. The study Sponsor or its designated representative will conduct device reconciliation during monitoring, the completion of subject enrollment, and at the conclusion of the study.

4. Study Overview

The Sponsor plans to conduct a clinical trial of the baroloop System. The study plan was developed according to the guidance given by EN ISO 14155 and the Declaration of Helsinki. The rationale for the trial design, endpoints and variables selected for study are described below. The justification for the study design and the content of the study are fully described below.

4.1. Study Design

The baroloop Study is a First in Human (FIH) study of the safety and feasibility of using the baroloop System in subjects with uncontrolled hypertension. As described above, an adequate body of historical data pertaining to device-based treatment of uncontrolled hypertension exists against which neuroloop can test the safety and performance of the baroloop System in a FIH study.

As described in the Background for the current study, the appropriate safety endpoint is defined by the occurrence of device- and treatment-related (both procedural and postprocedural) adverse events. Previous studies have used a similar definition of safety and, therefore, results of these previous studies provide useful historical comparison data to evaluate the safety of the baroloop System. Similarly, feasibility is defined as the ability to implant the baroloop Cuff electrode and IPG, and the ability to reduce blood pressure by VNS. The secondary objective is to document the effect of the baroloop device on the blood pressure and quality of life in subjects with hypertension.

4.2. Primary Study Endpoints

4.2.1. Safety

Composite Major Adverse Event (MAE) Rate at six (6) months post-treatment including:

- All-causes of death
- Hospitalization for hypertensive crisis post-titration
- Any device or procedure-related serious adverse event

All MAEs will be adjudicated by an independent Data Safety Management Board (DSMB).

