Figure 1: Schematic of the elementary parameterization of a stimulation pulse	22
Figure 2: baroloop Trial Screening and Enrollment Scheme	38

 neuroloop	Confidential	Protocol – The baroloop Study
--	---------------------	-------------------------------------

1. Protocol Synopsis

Sponsor	neuroloop GmbH [name] [name] Germany [contact] Email: [contact] Website: www.neuroloop.de
Principal Investigators	
Netherlands:
 [name] Division Internal Medicine and Dermatology Dept. of Vascular Medicine UMC Utrecht [name] [name]
	
Germany:
 Univ. [name]. med. [name] Experimentelle Gefäßmedizin und Transplantationsforschung Klinik für Nieren- und Hochdruckerkrankungen Medizinische Hochschule Hannover [name] [name]
Sponsor Representative	MAXIS Medical GmbH
	[name]
	[name]
	Germany
	[contact]
	[contact]
	Email: [contact]
Medical Monitor	[name].
	Chief Medical Officer
	MAXIS Medical GmbH
Protocol Title	A First in Human Study of Safety and Feasibility of baroloop
Short Title	The baroloop Study
Protocol number	Protocol Number: BL_CIP-FIH
	Revision: 2.4
	Date: 03 March 2021
Device	baroloop System
Indication for Use	The baroloop System is intended to be used to treat hypertension.

Objectives	
The primary objectives are to assess the safety and feasibility of the baroloop device for the treatment of subjects with hypertension (HTN).
 
The secondary objective is to document the effect of the baroloop device on the blood pressure and quality of life in subjects with hypertension (HTN).

Study Design	Non-randomized, prospective, single-arm, multi-center feasibility trial for subjects with hypertension
Number of Subjects	Up to ten (10) subjects
Number of Sites	Up to three (3) centers in Europe
Primary Safety Endpoint	
Composite Major Adverse Event (MAE) Rate at six (6) month post-treatment including:
 
• All causes of death• Hospitalization for hypertensive crisis post-titration• Any device or procedure-related serious adverse event 
All MAEs to be adjudicated by an independent Data Safety Management Board (DSMB).

Primary Feasibility Endpoint	The ability of the baroloop System to be placed around a vagal nerve and to stimulate at Day 14/21 post-implantation.

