4.2.2. Feasibility

The ability of the baroloop Systems to be placed around a vagal nerve and the ability to stimulate at Day 14/21 post-implantation.

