4.25. Follow-up titration every 7 days (\pm 2-3 days)

- Clinical assessment of the subject;
- Physical examination;
- Changes of medication regimen;

 neuroloop	Confidential	Protocol – The baroloop Study
--	---------------------	-------------------------------------

- Review and assessment of adverse events;
- Office cuff blood pressure; and
- Titration of vagal nerve stimulation should be repeated weekly to achieve up to a 20% reduction in systolic blood pressure or office BP < the age-adjusted 2018 ESC/ESH treatment target office blood pressure (OBP), whichever blood pressure achieved during stimulation is lower. The titration protocol described above should be followed each time the patient returns for adjustment of baroloop stimulation. The data from the IPG will also be downloaded at each visit for subsequent analysis.

4.26. 30-Day Follow-up Visit (+7 / -7 days)

- Clinical assessment of the subject;
- Physical examination;
- Changes of medication regimen;
- Review and assessment of adverse events;
- Office cuff blood pressure;
- Medication compliance testing;
- 24hr ABPM after observed therapy for hypertension;
- Quality of Life SF-36 questionnaire; and
- Further testing and titration of stimulation to achieve an OBP less than the age-adjusted target of hypertension treatment, as described in the titration directions.

4.27. 90-Day Follow-up Visit (+14 / -14 days)

- Clinical assessment of the subject;
- Physical examination;
- Changes of medication regimen;
- Review and assessment of adverse events;
- Office cuff blood pressure;
- Medication compliance testing;
- 24hr ABPM after observed therapy for hypertension;
- Quality of Life SF-36 questionnaire; and
- Further testing and titration of stimulation to achieve an OBP less than the age-adjusted target of hypertension treatment, as described in the titration directions

4.28. 180-Day Follow-up Visit (+14 / -14 days)

- Clinical assessment of the subject;
- Physical examination;
- Changes of medication regimen;

 neuroloop	Confidential	Protocol – The baroloop Study
--	---------------------	-------------------------------------

- Review and assessment of adverse events;
- Office cuff blood pressure;
- Medication compliance testing;
- 24hr ABPM after observed therapy for hypertension;
- Quality of Life SF-36 questionnaire; and
- Further testing and titration of stimulation to achieve an OBP less than the age-adjusted target of hypertension treatment, as described in the titration directions

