6.2. Primary Safety Endpoint

The primary safety endpoint is:

Composite Major Adverse Event (MAE) Rate at six (6) months post-treatment including:

- All-causes of death

 neuroloop	Confidential	Protocol – The baroloop Study
--	---------------------	-------------------------------------

- Hospitalization for hypertensive crisis
- Any device or procedure-related serious adverse event

All MAEs to be adjudicated by an independent Data Management Safety Board (DSMB).:

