6.3. Primary Feasibility Endpoint

The primary feasibility endpoint is technical success, defined as the ability of the baroloop System to be placed around a vagal nerve and the ability to stimulate at 14 days post-implantation.

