6.4. Secondary Endpoints

- The change in blood pressure recorded during intraoperative stimulation at the time of implantation.
- Mean reduction in 24-hour ambulatory systolic and diastolic blood pressure (ambulatory blood pressure monitoring - ABPM) at one (1), three (3), six (6), twelve (12) and eighteen (18) and twenty-four (24) months post-treatment versus baseline.
- The composite MAE rate at 1, 3, 6, 12, 18 and 24 months post-procedure defined:
 - All-causes of death
 - Hospitalization for hypertensive crisis post-titration
 - Any device or procedure-related serious adverse event
- The mean reduction in office diastolic and systolic blood pressure, and diastolic and systolic blood pressure at 1, 3, 6, 12, 18, and 24 months.
- Changes in antihypertensive medicines/doses through 1, 3, 6, 12, 18 and 24 months post-implantation as analyzed by Daily Defined Dosages (WHO Definition) and total medications.
- Quality of Life as measured by the Medical Outcomes Study 36-Item Short-Form Health Survey (SF-36).

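### SAP 6.2 and 6.3 word the two primary endpoints differently from the protocol: 6.2 omits the post-titration limit on crisis hospitalization, and 6.3 says 14 days where 4.2.2 says Day 14/21

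*Combined protocol and SAP*

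**What the plan says.** **Safety.** The MAE composite is stated six times. The synopsis (primary and secondary), 4.2.1, 4.3 and SAP 6.4 all word the second component as "Hospitalization for hypertensive crisis post-titration". SAP 6.2, which states the primary endpoint for analysis, has "Hospitalization for hypertensive crisis" and nothing more. The time point in 4.2.1 and 6.2 is given as "Composite Major Adverse Event (MAE) Rate at six (6) months post-treatment including". SAP 6.4 adds "The composite MAE rate at 1, 3, 6, 12, 18 and 24 months post-procedure defined", so it too reports a 6-month rate.

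No section defines when the post-titration period starts. Titration runs in repeated sessions (4.24), and the 180-day visit (4.28) still lists "Further testing and titration of stimulation to achieve an OBP less than the age-adjusted target of hypertension treatment".

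**Feasibility.** The synopsis requires the system "to be placed around a vagal nerve and to stimulate at Day 14/21 post-implantation", and 4.2.2 requires "the ability to stimulate at Day 14/21 post-implantation". SAP 6.3 calls the endpoint technical success and requires "the ability to stimulate at 14 days post-implantation". The Procedural Success entry in section 12 also uses 14 days. Section 4.23 allows the first titration no earlier than Day 14 and, for a subject not yet ready, as late as Day 21.

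**Analysis set.** SAP 6.1 says that the primary endpoints are analysed by intent to treat in all enrolled subjects. The next sentence restricts the primary analysis to subjects with technical success. SAP 6.6 rules out imputation and uses available data only.

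**Visit window.** The 14-day visit is +2/-3 days in the synopsis and 4.23, and +/-3 days in Table 3.

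**The concern.** Each primary endpoint has two wordings, and no text says which prevails. For safety, the primary rate under 6.2 and the 6-month rate under 6.4 share a name but may differ. Putting *post-titration* back into 6.2 would not be enough, because the term has no start date. For feasibility, a subject managed as 4.23 allows could be a success under one definition and not under the other. Because 6.1 ties the primary analysis to technical success, the wording of 6.3 also decides who is in that set.

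At stake are the two headline results of a study with at most 10 subjects, and their planned qualitative comparison with historical device therapies.

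**Working it through.** The plan gives no figure to reproduce: it states no hypothesis test and no power calculation (6.1). The check sets the texts side by side and adds day and count arithmetic. The event counts below are assumed.

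**Step 1. Which events change status under 6.2 against 6.4?** A fatal crisis counts as a death. A crisis related to the device or procedure counts under the third component. What remains is a non-fatal crisis hospitalization judged unrelated to both, occurring before titration or, on some readings, during it.

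**Step 2. How long is the excluded period?** Assume that the clock starts at implantation and that 6 months is 180 days.
- *Post-titration* read as after the first session, on Day 14 to 21 (4.23): 14/180 = 7.8% to 21/180 = 11.7%.
- Read as after the target is reached, it is longer and varies by subject. As an illustration, take the 12 weekly sessions named in 4.24. The last falls on Day 14 + 11 x 7 = 91, or Day 21 + 11 x 7 = 98. The excluded share is 91/180 = 50.6% or 98/180 = 54.4%.

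**Step 3. Effect on the safety rate.** With 10 subjects and one affected crisis as the only event, 0/10 = 0% (exact 95% interval 0 to 30.8%) becomes 1/10 = 10% (0.3 to 44.5%).

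**Step 4. Which days are in dispute for feasibility?** Section 4.23 permits first titration on Days 14 to 21, which is 21 - 14 + 1 = 8 days. SAP 6.3 contains no window. Read literally it covers Day 14 only, leaving 7 of the 8 permitted days (15 to 21) as success under 4.2.2 but not under 6.3.

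**Step 5. Effect on the feasibility rate.** One such subject among 10, all others succeeding: 10/10 = 100% (69.2 to 100%) under 4.2.2 and 9/10 = 90% (55.5 to 99.7%) under a literal 6.3, with all enrolled subjects in the denominator.

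**Step 6. Effect through 6.1.** If that subject lacks technical success under 6.3, the technical-success set has 9 members instead of 10. One MAE in another subject is then 1/10 = 10.0% or 1/9 = 11.1%. If the only MAE was in the subject who leaves, it is 1/10 = 10.0% or 0/9 = 0%.

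**Step 7. Is a decision rule affected?** The success statement in 6.1 uses failures to implant, a safety level judged by the DSMB, and any reduction in blood pressure. Section 9.13 uses DSMB judgement of the MAE rate and the count of implant failures. Neither sets a numeric limit on the MAE rate or on stimulation at Day 14 or Day 21.

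**The case against.** The case for treating this as editorial is fair. The study is descriptive, and a 10-point shift is simply one subject in ten for an assumed event. Section 4.23 makes the intent of Day 14/21 fairly clear. It also lists initial testing beside titration and defers only the titration, so a deferred subject might still be tested at Day 14. Procedural Success in section 12 is not an endpoint. All of this stands and limits the weight of the point. It does not settle which text applies, and 4.23 does not say whether a Day-14 test takes place when titration is deferred.

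A reader might also infer more than the documents support:
- **That the limit could exclude all 180 days, because titration is listed at 4.28.** That entry follows the titration directions, under which no further titration is needed at or below target (4.24). Table 3 marks later titration as done if necessary, and 4.24 expects most patients to need few sessions.
- **That the safety discrepancy disappears because *post-treatment* runs from first stimulation.** No passage ties it to that. The synopsis labels the follow-up visits *post-procedure*, and 4.3 uses the terms interchangeably.
- **That a deferred subject would simply drop out, giving 9/9.** SAP 6.6 alone might suggest this, but the intent-to-treat sentence in 6.1 includes all enrolled subjects.
- **That the visit window settles which days 6.3 covers.** SAP 6.3 does not refer to any window.
- **That the DSMB would miss some crises.** In-patient hospitalization is an SAE criterion (7.2), and every SAE is DSMB-adjudicated (section 7).

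**Conclusion.** The inconsistency is real and should be corrected, but its reach is narrow. SAP 6.2 is the only one of six statements without the post-titration limit, so the SAP defines two 6-month MAE rates. They differ only for non-fatal, unrelated crises before titration or, depending on the reading, during it. The excluded period is 8 to 12% of the 180 days under the first-session reading with the clock at implantation. It is longer if the term means after the target is reached. Those crises remain adjudicated SAEs either way.

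SAP 6.3 can classify a subject managed within 4.23 differently from 4.2.2, and through 6.1 can remove that subject from the stated primary analysis set. This half has the wider consequence.

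With 10 subjects, one such case moves a primary rate by 10 points. A reader might infer that study success or early stopping turns on the wording. It does not, since no numeric rule uses either rate. That the version would be chosen after seeing the data is a possibility left open, not something the documents indicate. The wording differences are certain; the sizes rest on assumed events and on the stated clock and reading.

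**What to change.** Before any data are reviewed:

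1. Change SAP 6.3, and for consistency Procedural Success in section 12, to Day 14/21 to match 4.2.2. State that under the intent-to-treat analysis in 6.1 an enrolled subject without demonstrated stimulation by Day 21 counts as a failure, notwithstanding 6.6.
2. Use one MAE definition throughout. Restoring *post-titration* in 6.2 is the smallest change, since the other five statements carry it. Define it by a recorded start date, for example the date of the first titration session, and state when the 6-month clock starts. Tabulate crisis hospitalizations before and after that date so that both rates can be seen.
3. Reconcile the 14-day visit window in Table 3 with the synopsis and 4.23.

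The cost is wording changes and one small table from data already collected. The downside is that early crises unrelated to device and procedure then appear only in that table and in the SAE listings, not in the primary rate.
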